# **Study Protocol and Statistical Analysis Plan**

## **Body and Social Behavior**

**NCT number** NCT05654441

**Document Date** 07/19/2024

**INFLUENCE OF MILD INFLAMMATORY CHALLENGE ON CYTOKINES, AFFECT, AND SOCIALITY IN HUMANS; A RANDOMIZED CONTROLLED TRIAL USING THE INFLUENZA VACCINE.**

[name], [name], [name], [name], [name], [name]

University of North Carolina at Chapel Hill, Department of Psychology and Neuroscience

University of Michigan, Department of Psychology

**1. Description:** This parallel-arm double-blind placebo-controlled randomized clinical trial examined the influence of a mild inflammatory challenge (the influenza vaccine) on various aspects of human affect, social perception, and sickness symptoms. *Please note, as this project was designed to address several scientific aims – we have chosen to submit an initial pre-registration of methods. Specific hypotheses and statistical tests will be outlined in amendments to this pre-registration.*

## **2. Design**

**Overview of Study design:** Participants completed two in-person study sessions ~24 hours apart. All study visits were scheduled in the morning (7:00 AM – 11:00 AM). During the first session (1-hour), participants completed informed consent, a self-report baseline questionnaire, and a heartbeat counting task. They also provided a baseline blood sample, collected via venipuncture, and were administered an injection of either the active influenza vaccine or a sham vaccine (saline solution). During the second session (2-hours), participants again completed self-report questionnaires and had their blood taken via venipuncture. They then completed three tasks: a sociogram task, two social interaction tasks, and a bargaining game task. Participants were then debriefed and compensated \$25/hour.

**Study type:** Experiment

**Randomization & Blinding:** Simple condition random assignment was implemented by UNC's Investigational Drug Services (IDS) pharmacy. Pre-filled (unlabeled) syringes were delivered by IDS to the University of North Carolina at Chapel Hill's Clinical and Translational research center (CTRC) in opaque stapled bags. These bags were opened by trained CTRC nursing staff—who dispensed the doses—immediately prior to drug injection. Primary research staff were not present for drug injection and participants were asked to look away during injection (and never saw the syringes) to maintain blinding.

## **3. Sampling Plan**

**Existing data:** As of the date of submission, the data exist, and we have accessed it.

[figure not shown]
### **Explanation of existing data:**

- A combination of t-tests and chi-squared tests were conducted to assess for any failure in random assignment. Variables assessed included: Age, Assigned Sex at Birth (ASAB), Gender, Sexual Orientation, Race/Ethnicity, Annual Household Income, Subjective Socioeconomic Status, Depressive Symptoms, Perceived Stress, Sleep Health, menstrual status, use of birth control, waist-hip ratio, mental health diagnoses, use of mood-altering medications, baseline levels of circulating cytokines, and non-compliance with instructions to refrain from alcohol use taking OTC medications prior to study sessions.

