**2. Analysis Plan**

**Statistical models:** Statistical models will assess 5 broad scientific aims.

**Scientific Aim 1: Inflammatory Cytokines.** To test whether treatment groups differed in circulating levels of pro-inflammatory cytokines following vaccine administration, we will run repeated-measures analyses of variance (RM-ANOVA; Winkens et al 2007). Inflammatory cytokines at both sessions will be treated as the criterion, session number (i.e., time) will be treated as a within-subjects predictor, and condition assignment (placebo vs. influenza vaccine) will be treated as a between-subjects predictor. RM-ANOVA models will be run separately for each of the four inflammatory cytokines assayed. Significance will be assessed at  $p<0.05$ . We hypothesize a significant interaction between condition and time on inflammation such that participants in the influenza condition will have higher levels of all four markers of inflammation than participants in the placebo condition at session 2 but not at session 1.

**Scientific Aim 2: Sickness Symptoms.** To test whether treatment groups differed in sickness symptoms following drug administration, we will complete a series of analytic steps:

1. Given that the Sickness Symptom Questionnaire (SicknessQ) has primarily been validated in samples treated with endotoxin (a potent inflammatory challenge), we will begin by conducting confirmatory factor analysis with 1 factor on scale items. Good model fit for CFA will be represented by  $RMSEA \leq .08$ ,  $CFI \geq .95$ , and  $TLI \geq .90$  (Hu & Bentler, 1999; Schreiber, Nora, Stage, Barlow, & King, 2006). We will then run t-tests to assess for group differences in overall sickness symptom scores. Significance for t-tests will be assessed at  $p<0.05$ .
2. We will also run separate two-tailed independent-samples t-tests to assess for group differences in individual sickness symptoms (i.e., each item of the SicknessQ). Significance will be assessed at  $p<0.05$ .
3. Finally, we will run two additional two-tailed independent-samples t-tests to assess for group differences in endorsements of two physical symptoms not included in the SicknessQ but commonly assessed when using this and similar methods (Eisenberger et al., 2009; Kuhlman et al., 2018): “*fatigue*” and “*muscle aches/pain*.” Significance will be assessed at  $p<0.05$ . Significance will be assessed at  $p<0.05$ .

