**Scientific Aim 3. Affect.** To test whether treatment groups differed in felt affect following vaccine administration, we will run 4 two-tailed independent-samples t-tests to assess for group differences in positive high arousal (PH) affect, positive low arousal (PL) affect, negative high

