## BODY AND SOCIAL BEHAVIOR (BSB)

(NH) arousal affect, and negative low (NL) arousal affect respectively. PH, PL, NH, and NL will be computed using the Positive and Negative Affect Schedule (PANAS) word endorsements. Specifically, PH will be operationalized as the mean endorsement across items: *amused, determined, enthusiastic, excited, happy, inspired, proud, strong, active, and alert*. PN will be operationalized as the mean endorsement across items: *Angry, Irritable, Nervous, Scared, Upset, Afraid, Ashamed, Distressed, Frustrated, Hostile, and Jittery*. NL will be operationalized as mean endorsement across items: *bored, guilty, sad, and worn out*. PL will be operationalized as mean endorsement across items: *attentive, calm, interested, grateful, and relieved*. Significance for t-tests will be assessed at  $p<0.05$ .

**Scientific aim 4. Sleep.** We will run three two-tailed independent-samples t-tests to assess for group differences in the subsequent night's sleep following vaccine-administration. First, we will assess for group differences in that night's sleep as operationalized using an index of items adapted from the Brief Pittsburgh Sleep Quality Index. These five items assess five facets of sleep—quality, quantity, daytime dysfunction, latency, and nighttime awakenings—and will be combined into a “Sleep Quality Index.” Next, we will run two additional models testing for group differences in two facets, subjective sleep quality (1-item) and subjective quantity (1-item), separately. Significance for all t-tests will be assessed at  $p<0.05$ .

**Scientific Aim 5. Social Connection.** We will run a two-tailed t-test to assess for group differences in felt social connection. Social connection will be operationalized as averaged scores on 10-items assessing feelings of social disconnection. Significance for t-tests will be assessed at  $p<0.05$ .

**Scientific Aim 6: Models using continuous measures of circulating cytokines.** To assess evidence for dose-dependency effects between circulating cytokines and outcomes-of-interest (same outcomes described in scientific aims 2-5), we will conduct a series of linear regression models using data from only the subset of participants assigned to the influenza vaccine condition ( $n=52$ ). Models will be run separately for each outcome-of-interest and for each cytokine and will take the general form:

1.  $outcome_i = \beta_0 + \beta_1(\Delta \text{inflammation}) + \beta_2(BL \text{inflammation})$

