## BODY AND SOCIAL BEHAVIOR (BSB)

$n_{participants}=102$ ,  $r=0.5$ , suggested that we would be adequately powered to observe a medium effect size  $f^2=0.14$ .

Sensitivity Analysis for t-tests: Sensitivity analysis conducted in g\*power for a two-tailed t-test (independent means) with  $\alpha=0.05$ ,  $(1-\beta)=0.80$ ,  $n_1=50$ ,  $n_2=52$  suggested that we would be adequately powered to observe a medium effect size  $d=0.56$ .

Sensitivity Analysis for linear regression: Sensitivity analysis for simple regression (fixed model, single regression coefficient) for a two-tailed t-test with  $\alpha=0.05$ ,  $(1-\beta)=0.80$ ,  $n_{participants}=52$ , and  $n_{predictors}=4$  suggested that we would be adequately powered to observe a medium effect size  $f^2=0.16$ .

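### Aims 2–5 compare the arms by unadjusted t-tests although relevant session-1 measures are held; the baseline balance tests are no substitute for fixed covariate adjustment

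*Combined protocol and SAP*

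**What the plan says.** Allocation (section 2, Randomization & Blinding): "Simple condition random assignment was implemented" by the pharmacy. No stratification or blocking is described.

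Balance (section 3, Explanation of existing data): "A combination of t-tests and chi-squared tests were conducted to assess for any failure in random assignment". The list begins "Variables assessed included: Age, Assigned Sex at Birth (ASAB), Gender, Sexual Orientation, Race/Ethnicity, Annual Household Income" and goes on to depressive symptoms, perceived stress, sleep health, baseline cytokines and others. No significance level, multiplicity rule, result or consequence is given. Loneliness is not on the list.

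Outcome analyses (Amendment 1, section 2):
- Aim 1 uses both sessions in a repeated-measures model.
- Aim 2 uses t-tests on the overall SicknessQ score, on each of its items, and on fatigue and muscle aches.
- Aim 3: "we will run 4 two-tailed independent-samples t-tests to assess for group differences in positive high arousal (PH) affect" and the three other affect scores.
- Aim 4 uses three t-tests on sleep.
- Aim 5: "We will run a two-tailed t-test to assess for group differences in felt social connection".
- Covariates appear only in Aim 6, which uses the vaccine arm alone and so compares no arms.

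Session-1 measures (section 4) include SicknessQ, the adapted brief PSQI, valence, arousal, the PHQ-9 and the Revised UCLA Loneliness Scale. The modified PANAS, the social-disconnection items and the physical symptom endorsements are listed at session 2 only.

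**The concern.** A trial of about 100 people under simple randomisation can have noticeable chance differences between arms on any one baseline variable. Where a variable predicts the outcome, leaving it out costs precision in every case, and leaves the estimate shifted in a trial where the variable happens to be unbalanced.

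No between-arm model in Aims 2–5 uses a session-1 measure. For Aims 2 and 4 this means that scores on the same instrument are set aside. For Aims 3 and 5 no session-1 score of the outcome exists, so adjustment needs a proxy chosen on content. The only use of baseline data across the arms in these aims is the set of balance tests. A reader who takes non-significant results there as showing the arms comparable would be reassured more than the sample size allows.

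**Working it through.** **Inputs**
- Arm sizes 50 and 52, two-sided 0.05, 80% power, detectable d=0.56: Amendment 1, Power (t-tests).
- Threshold for the balance tests: not stated; assumed 0.05 two-sided.
- Correlation r between session-1 covariate and session-2 outcome: not stated; range 0.3–0.6 assumed.

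**1. The plan's own figure.** Standard error of a standardised difference = √(1/50 + 1/52) = 0.198 SD. At d=0.56 the noncentrality is 0.56/0.198 = 2.83. With 100 degrees of freedom the noncentral t gives power 0.7996, and 80% is reached at d=0.5603. The stated 0.56 reproduces.

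**2. What a non-significant balance test allows.** Critical t is 1.984, so the largest observed imbalance that passes is 1.984 × 0.198 = 0.393 SD. An observed difference of 0.5 SD gives t = 0.5/0.198 = 2.52, p=0.013, and is flagged. Under sound randomisation a given continuous variable differs by at least 0.30 SD in about 13% of allocations. Removing the 5% that are flagged leaves about 8% with an unflagged imbalance of 0.30–0.39 SD.

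**3. Effect on an unadjusted comparison at that limit.** Shift in the outcome difference = r × 0.393. Given the imbalance, the test statistic under no effect has mean m = r × 0.393/0.198 and SD s = √(1 − r²). The conditional type I error is P(Z > (1.96 − m)/s) + P(Z < (−1.96 − m)/s).

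**4. Gain from adjusting for one covariate.** Residual SD falls to s, so the effective standardised effect is 0.56/s, and the detectable effect becomes 0.56 × s. Power is from the noncentral t with 99 degrees of freedom.

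| r | Shift (SD) | m | s | Conditional type I error | Detectable d | Power at d=0.56 |
|---|---|---|---|---|---|---|
| 0.3 | 0.12 | 0.60 | 0.954 | 8.0% | 0.53 | 84% |
| 0.4 | 0.16 | 0.79 | 0.917 | 10.3% | 0.51 | 86% |
| 0.5 | 0.20 | 0.99 | 0.866 | 13.2% | 0.48 | 90% |
| 0.6 | 0.24 | 1.19 | 0.800 | 16.8% | 0.45 | 94% |

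Using 1.984 in place of 1.96 gives 7.6%, 9.8%, 12.6% and 16.1%. The shifts are 21–42% of d=0.56 (0.118/0.56 to 0.236/0.56).

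These error rates apply at the edge of the non-significant range. Averaged by simulation over unflagged imbalances of 0.30–0.39 SD they are 8.4%, 10.2% and 12.1% at r = 0.4, 0.5 and 0.6. Averaged over all randomisations the rate is 5.0%.

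**5. Several covariates.** Where more than one is used (Aim 3), r is read as the multiple correlation. With three covariates the degrees of freedom are 97, and power at 0.5 is still 90%.

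**The case against.** The balance paragraph is a past-tense disclosure, not a decision rule. It sets no threshold, draws no conclusion, selects no covariate, and does not claim that the arms are equivalent. That stands, so the point here is the missing adjustment and not a fault in the disclosure.

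Randomisation already protects the t-tests: their 5% error allows for chance imbalance. That also stands. What they lack is protection conditional on an imbalance that did occur, and precision. Amendment 1 also plans analyses that exclude people with a depression diagnosis, SSRI use or non-compliance. They are printed after Aim 6, so their reach is unclear, and exclusion is not adjustment.

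Four stronger readings are tempting and are not supported:
- *The balance tests miss a 0.5-SD chance imbalance 29% of the time.* The 29% (1 − 0.705) is the miss rate for a true population shift, as from broken allocation. An observed 0.5-SD difference would be flagged at 0.05.
- *They raise a false alarm in about 6 of 10 sound trials.* Independent tests at 0.05 give 58% for 17 variables (1 − 0.95^17) and 66% for 21. Both the threshold and independence are assumed, and the listed variables are related: at a pairwise correlation of 0.3 the figure is 49% for 17. Pre-session-2 non-compliance is also not a baseline variable.
- *Aims 3 and 5 alone are exposed, with no other protection.* Aims 2 and 4 are equally unadjusted, and randomisation protects all four on average.
- *The registered tests are invalid.* They are not.

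A last objection is that covariates chosen now come after data access. Section 3 states that session-2 group differences in sickness behaviour, social connection, valence and arousal had already been tested for a poster. This is a real limit, and it is why the added models cannot replace the registered tests.

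**Conclusion.** The concern holds as a missed opportunity for precision and for protection against a realised imbalance, across Aims 2–5. The 0.39-SD limit follows from the arm sizes and an assumed 0.05 threshold. The shift of 0.12–0.24 SD, the conditional error of about 8–17% and the power of about 84–94% also rest on an assumed correlation of 0.3–0.6. A weaker covariate would gain less. The documents do not show that any imbalance occurred, and the power gain does not depend on one. The change is worth making because the data are already held and the work is small.

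**What to change.** Keep every registered t-test as the lead analysis. Beside each, add a linear model of the session-2 outcome on arm plus covariates fixed now, on content:
- **Aim 2:** session-1 SicknessQ score (the same item for item-level tests; the overall score as proxy for fatigue and muscle aches, which have no session-1 rating).
- **Aim 3:** session-1 valence, arousal and depressive symptoms.
- **Aim 4:** the matching session-1 score from the adapted brief PSQI.
- **Aim 5:** Revised UCLA Loneliness score.

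Use these covariates whatever the balance p-values, and let no balance test add or remove one. Report the unadjusted and adjusted estimates together with confidence intervals. Label the models supplementary and added after data access, and refer to the group tests already run for the poster. Reporting baseline differences as standardised differences is optional, since it changes no result.

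Cost: a short paragraph in the amendment; 11 extra fits (three in Aim 2, four in Aim 3, three in Aim 4, one in Aim 5) plus one per SicknessQ item; one degree of freedom per covariate out of about 100. The main downside is the post-access label, which limits the weight the adjusted estimates can carry.

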### Sample size:

**Sample size rationale:** A priori, we aimed to recruit 100 individuals (~50 females) ages 18-35. This sample size was selected based on a power-analysis conducted in G\*Power (Faul et al 2007) indicating that a minimum of 90 participants (45 per condition) were necessary to achieve 80% power to detect a medium effect size of  $F^2=.15$  for a within/between-subjects interaction (2 groups; 2 repeated measurements; 0.5 correlation between measures). We aimed to collect 100 instead of 90 in case of data loss due to, for example, participants not returning to the lab for their post-vaccine session.

**Stopping rule:** We concluded the study after reaching our target recruit goal (N=100), which happened to coincide with the start of the university's winter break, meaning clinics and services

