### Power:

Sensitivity Analysis for RM-ANOVA: See “sample size rational” in main study pre-registration. Sensitivity analyses conducted in g\*power (Faul et al 2007) for ANOVA (repeated measures, within-between interaction) with  $\alpha=0.05$ ,  $(1-\beta)=0.80$ , number of  $n_{\text{groups}}=2$ ,  $n_{\text{measurements}}=2$ ,

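### The repeated-measures effect sizes printed as F²=.15 and f²=0.14 are values of f, not f²; the label understates the design's sensitivity, and the sample size stands.

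*Combined protocol and SAP*

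**What the plan says.** Section 3 (Sampling Plan), under the sample size rationale, reports a G*Power calculation in which "a minimum of 90 participants (45 per condition) were necessary to achieve 80% power". The effect size is introduced as "80% power to detect a medium effect size of $F^2=.15$ for a within/between-subjects interaction". The other inputs are two groups, two measurements and a correlation of 0.5. No alpha is given there. The target was then raised to 100 to allow for data loss.

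Amendment 1, under Power, reports three sensitivity analyses:

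- The first is "for ANOVA (repeated measures, within-between interaction) with $\alpha=0.05", power 0.80, two groups, two measurements, 102 participants and r=0.5. Its result is that "we would be adequately powered to observe a medium effect size $f^2=0.14".
- The second is a two-tailed t-test with 50 and 52 participants. Its result is that "we would be adequately powered to observe a medium effect size $d=0.56".
- The third is a linear regression with 52 participants and four predictors. Its result is that "we would be adequately powered to observe a medium effect size $f^2=0.16".

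Neither place says that the repeated-measures values are f rather than f².

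**The concern.** Cohen's f and f² are different scales. An f² of .15 corresponds to f=.387, a large difference in pre-post change for a design with two measurements correlated at 0.5. It is hard to see why 90 people would be needed to detect it.

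The sample size rationale is the only justification of N, and the first sensitivity analysis is the only statement of what the Aim 1 condition-by-time test can detect. Anyone who checks N from the printed value gets a very different answer and may doubt a calculation that is sound. Anyone interpreting a null cytokine result from the printed value would conclude that moderate effects could easily have been missed. The same symbol also appears on the regression line, where it means what it says, so a reader cannot tell which scale applies.

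**Working it through.** **Inputs.** Groups k=2, measurements m=2, r=0.5 and power 0.80, from the sample size rationale and again from Amendment 1. N is 90 (rationale) and 102 (amendment). Alpha is 0.05, stated in Amendment 1 and assumed to apply to the rationale as well.

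**Formula.** For the within-between interaction, the F test has (k−1)(m−1)=1 and (N−k)(m−1)=N−2 degrees of freedom. Its noncentrality is λ = f²·N·m/(1−r) = f²·N·2/0.5 = 4·f²·N.

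**Step 1: the plan's N, reading .15 as f.** Here f²=.15²=.0225, and at N=90 λ = 4×.0225×90 = 8.1. Power is .795 at N=88, .799 at N=89 and .804 at N=90. The minimum is exactly 90, as the plan states.

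**Step 2: the plan's N, reading .15 as f².** At N=16, λ = 4×.15×16 = 9.6. Power is .792 at N=15 and .821 at N=16, so the minimum is 16. Power at N=90 exceeds .9999.

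**Step 3: the amendment's figure.** N=102 is an input here, and the detectable effect is the output. Solving for 80% power gives f=0.1400, or f²=0.0196 (λ = 4×.0196×102 = 8.00). The printed digits are the value of f. This step uses no borrowed alpha.

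**Step 4: comparison with the plan's own t-test line.** With two groups and two times, the interaction test is a two-sample t-test on change scores. The arms differ in mean change by 4f standard deviations of a single measurement. The SD of change is √(2(1−r)) = 1 such SD at r=0.5, so d=4f.

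| Reading | Difference in change (SD, r=0.5) |
|---|---|
| f=0.14 | 4×0.14 = 0.56 |
| f²=0.14 | 4×√0.14 = 1.50 |
| f=.15 | 4×.15 = 0.60 |
| f²=.15 | 4×√.15 = 1.55 |

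The amendment's t-test with 50 and 52 participants has a detectable d of .5603, which reproduces its printed 0.56. Only f=0.14 agrees with it.

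**Step 5: the regression line.** With n=52, four predictors and λ=f²·n on (1, 47) degrees of freedom, the detectable f² is 0.157. At the printed 0.16, power is .807 if it is f² and .204 if it is f. This label is correct.

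**Step 6: can another convention rescue the f² label?**

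- If the correlation is left out (λ=f²·N or f²·(N−2)), f²=.15 needs 55 or 57 participants (56 or 58 with equal arms). The detectable f² at N=102 would be .078 or .080, not 0.14.
- The between-subjects form needs 42 for f²=.15.
- At alpha 0.10, 0.025 and 0.01, f²=.15 needs 12, 19 and 24.
- With r from 0 to 0.7, f²=.15 needs between 30 and 12.

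None gives 90. For f=.15, alphas of 0.10, 0.025 and 0.01 give 71, 109 and 134. Of the alphas tried, only 0.05 gives 90, which supports borrowing it.

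**The case against.** Four points can be made on the other side.

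*It changes nothing.* The error is conservative, recruitment is complete, the data have been accessed, and no analysis depends on the symbol. A careful reader could recover f=.15 from the inputs given, and d=0.56 already appears for the same participants. All of this is true, and it limits the seriousness. But the amendment does not link d=0.56 to the interaction test, and the only sample size justification should reproduce as written.

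*It may be an input error and not a label error.* The authors may have wanted f²=.15 and typed .15 into the field for f. Calling both .15 and the genuine regression f²=0.16 medium gives this some support. The documents cannot settle it, and the saved output would show f=.15 either way. This stands as an open question about intent for the rationale. It does not affect the correction: whatever was meant, 90 participants give 80% power at f=.15. The 0.14 in the amendment is an output of the calculation, so there the label alone is wrong.

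*The rationale states no alpha.* This also stands, but 0.05 is given for the same test in the amendment and returns exactly 90.

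*After correction, medium would describe f² values of about .02 and of 0.16.* That is so on the f² scale. In SD units the repeated-measures effects are 0.56 to 0.60, in line with the d=0.56 that the plan also calls medium, so the word is defensible there.

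**Conclusion.** The concern holds. Both repeated-measures effect sizes carry the wrong symbol. On the f² scale the printed values are too large by .15/.0225 = 6.7 times and 0.14/0.0196 = 7.1 times. On the f or SD scale the factor is about 2.6 to 2.7 (1.55 against 0.60 SD, and 1.50 against 0.56 SD). The label understates sensitivity. The minimum of 90, the target of 100 and every planned analysis are unaffected.

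The result for the rationale assumes alpha 0.05. The result for the amendment uses only stated inputs. The SD translations assume the planning correlation of 0.5. That N stands refers to a single interaction test at alpha 0.05; multiplicity across the four cytokines is a separate matter. This should be fixed, since it misstates a relied-on figure in two places, but it does not threaten the trial.

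**What to change.** Check the saved G*Power output, and have the sponsor confirm which effect was intended in the rationale. Then:

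- In the sample size rationale (section 3), replace F²=.15 with: f=.15 (f²=.0225; a 0.60 SD difference between arms in pre-post change, assuming r=0.5). State the alpha used.
- In Amendment 1, Power, repeated-measures line, replace f²=0.14 with: f=0.14 (f²=0.0196; 0.56 SD, assuming r=0.5).
- Leave the regression value f²=0.16 and the word medium as they are. The SD figures added above show the sense in which medium applies.

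The cost is two symbol corrections and one stated alpha. N, the target of 100 and the analyses do not change.
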